## 4 Study Design

This will be a multi-center randomized, unblinded clinical trial comparing Ablation to Anti-arrhythmic treatments for patients with first encounter for new symptomatic AF diagnosis within 12 months. Up to 220 patients will be enrolled over approximately 18 months.

## 5 Subject Selection

### 5.1 Subject Screening and Enrollment

The study will enroll patients with chronically impaired LV function on optimal medical therapy with first encounter for new symptomatic AF diagnosis within 12 months. Before any study tests or procedures take place, the subject will be asked to read and sign the informed consent form (ICF) that has been approved by the Institutional Review Board (IRB) / Ethics Committee. Previously evaluated subjects that meet amended study eligibility can be reconsidered for the trial. The complete informed consent process will include giving the subject adequate information about the study and ensuring that there is a sufficient amount of time to comprehend the information in the consent form and have all questions answered before making a decision to participate in the study. Enrollment will occur when a subject signs and dates an informed consent form and provides authorization to use protected health information.

## 5.2 Inclusion Criteria

---

Patients must meet all of the following criteria:

1. Be  $\geq 18$  years of age
2. Provide signed written Informed Consent
3. Symptomatic AF documented by ECG or heart rhythm monitoring within 12 months
4. Patients should be on optimal medical therapy for HF (heart failure) for 3 months prior to randomization. Adjustments to medications within this 3 month period are permitted.
5. Chronically impaired LV function defined as EF 20%-45% within the last 3 months by echocardiogram, nuclear imaging, MRI or cardiac catheterization
6. All patients should be on an optimal therapy for impaired LV function. Optimal therapy includes at least one ACE inhibitor or angiotensin receptor blockers (ARB) in ACE-intolerant patients along with beta blockers for at least 3 months. For those patients intolerant to ACE/ARB's, a combination of hydralazine and isosorbide dinitrate is recommended. NYHA class III patients may be prescribed spironolactone
7. Ability to complete 6 minute walk test
8. Be eligible for catheter ablation and anti-arrhythmic drugs

## 5.3 Exclusion Criteria

---

Patients must meet none of the criteria:

1. Women of childbearing potential (women will not be permitted to participate unless post-menopausal or surgically sterile)
2. Patients hospitalized for HF (heart failure) within the 3 months prior to randomization
3. Reversible causes of AF such as pericarditis, thyroid disorders, acute alcohol intoxication, recent major surgical procedures, or trauma
4. Recent Reversible LV impairment that may be attributed to AF with RVR and may improve with introduction of rate control.
5. Presently with Valvular Heart disease requiring surgical intervention
6. Presently with coronary artery disease requiring surgical or percutaneous intervention
7. Early Post-operative AF (within three months of surgery)
8. Previous MAZE or left atrial instrumentation (including ablation and Left Atrial Appendage exclusion)
9. History of AVN ablation
10. Hypertrophic Cardiomyopathy
11. Prolonged QT interval
12. Liver Failure
13. Renal Failure requiring dialysis
14. Social factors that would preclude follow up or make compliance difficult. History of drug, alcohol, or substance abuse as assessed by the investigator.
15. Contraindication to the use of anti-arrhythmic medications and/or appropriate anticoagulation therapy
16. Currently enrolled in, or discontinued within the last 30 days from a clinical trial involving an investigational product or non-approved use of a drug or device or concurrently enrolled in any other type of medical research judged not to be scientifically or medically compatible with this study.
17. Patients with severe pulmonary disease
18. Documented intra-atrial thrombus, tumor, or another structural abnormality which precludes catheter introduction
19. Unable or unwilling to comply with protocol requirements or deemed by the investigator to be unfit for the study.

CONFIDENTIAL

[figure not shown]
This document is confidential and the property of The Cleveland Clinic Foundation. No part of it may be transmitted, reproduced, published, or used by other persons without prior written authorization from the study sponsor.

V6.0\_22May2017

[figure not shown]
## 5.4 Randomization

Patients first encountered with recently diagnosed AF meeting the all of the inclusion criteria and none of the exclusion criteria and provided signed consent will be randomized in a 1:1 fashion (based on EF stratification EF  $\leq 35\%$  and  $>35\%$ ) into treatment by AF ablation or AADs. Patients already on dofetilide and randomized to ablation may continue taking dofetilide until 2 months post ablation. Other AADs will be stopped 1 week prior to ablation. Dofetilide may be initiated pre-ablation or post ablation but must be stopped 2 months post ablation.

### Anti-Arrhythmic Drug (AAD) Naïve patients:

### Patients already on AADs

CONFIDENTIAL

This document is confidential and the property of The Cleveland Clinic Foundation. No part of it may be transmitted, reproduced, published, or used by other persons without prior written authorization from the study sponsor.

V6.0\_22May2017

## 6 Study Procedures

The time course for the trial is divided into a treatment period followed by the trial period. The treatment period will include the first 3 months post enrollment or post procedure during which repeat ablation can be performed and titration of AAD dosages can be performed. The follow-up trial period will commence at end of treatment period and all outcome data will be collected over a 12 month period.

### 6.1 AF Ablation

Experienced electrophysiologists will perform the electrophysiological studies, mapping and ablation for Atrial Fibrillation per guidelines and Standard of care. Ablation targets will be determined by the investigator. Patients already on dofetilide and randomized to ablation may continue taking dofetilide until 2 months post ablation. Other AADs will be stopped 1 week prior to ablation. Dofetilide may be initiated pre-ablation or post ablation but must be stopped 2 months post ablation. Oral anticoagulation will follow AHA/ACC guidelines and will be continued after the PVI procedure for at least 6 months.

Any repeat ablations occurring during the treatment period should be captured on the CRF. If a spiral CT scan was performed, information should be recorded on the CRF. Outcomes will be collected. Primary outcome data in the ablation arm will only be included in the analysis after the treatment period (three months post randomization).

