## Study Synopsis

Title	Catheter Ablation vs. Medical Therapy in Congested Hearts with AF (CATCH-AF in Patients with impaired LV function)
Protocol Number	6.0
Study Treatment	Strategy of Early Atrial Fibrillation Ablation compared to conventional Anti-Arrhythmic Drug management.
Indication	Chronically impaired LV function on optimal medical therapy with first encounter for new symptomatic AF diagnosis within 12 months.
Study Design	This study is a, multi-center, randomized, unblinded, clinical trial with the objective of enrolling 220 patients over approximately 18 months.
Study Objectives	
 
• To determine if catheter-based atrial fibrillation (AF) ablation is superior to medical treatment in patients with impaired left ventricular function who have been diagnosed with symptomatic AF within the past 12 months
 
• Hypothesis: AF ablation is better than medical therapy for patients with symptomatic AF and impaired LV function in terms of recurrent and total number of hospitalizations, recurrence of AF, EF, quality of life, and 6-minute walk distance.
 

Primary Endpoint	The primary endpoint is time to first hospitalization (>24hr) for heart failure, recurrence of AF or DC cardioversion after the treatment period
Secondary Endpoint	Secondary endpoints will include evaluation of the following: 
 
• Total number of cardiovascular hospitalizations during the trial period for each group
 
• Time to Recurrence of AF lasting longer than 30 seconds
 
• Change in distance walked in 6-minute walk test
 
• Change in Rand 36-Item Health Survey (SF-36) during trial period
 
• Change in EF during trial period
 

Duration of Treatment and Study Period	The time course for the trial is divided into a treatment period followed by the trial period. The treatment period will include the first 3 months post enrollment. The trial period will commence at end of treatment period and all outcome data will be collected over a 12 month period.

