## Study Assessments:

Procedure	Screening/ Baseline/ Randomization Visit	3-6 month Follow-up Visit (+/- 3 weeks)	12-15 month Follow-up Visit (+/- 3 weeks)
Confirm Inclusion/Exclusion Criteria	X		
Obtain Informed Consent	X		
Verify that females are not of childbearing potential 	X		
Randomization	X		
Record Medical History and Physical	X		
Record Vital Signs HR/BP	X	X	X
Record Medications	X	X	X
Record ECG	X	X	X
Record Echocardiogram	X		X
6 minute walk test	X	X	X
Record Routine Lab Assessments	X	X	X
Record Clinically Indicated Tests	X	X	X
Rand 36-Item Health Survey (SF-36)	X	X	X
AFSS QOL	X	X	X
Assessment NYHA	X	X	X
Arrhythmia Monitoring	X	X	X
Assessment of SAE/AE		X	X
Assessment of Hospitalization		X	X

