## 3 Study Endpoints

Timeframe to endpoints: After the 3 month treatment period, the endpoints will be assessed for 12 months

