### 6.2 AAD Treatment

Patients randomized to AAD will receive AADs per Physician and patient preference. Initiation and ongoing clinical evaluations of drug therapy must conform to HRS/ACC/AHA/ ESC guidelines. Oral anticoagulation will follow HRS/ACC/AHA/ESC guidelines. If a patient randomized to the AAD treatment arm has an ablation during the treatment initiation period, the date of ablation will be recorded on the CRF. Outcomes will be collected after the optimization of AAD.

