### 6.4.2 12-15 Month Post Randomization Visit (+/- 3 weeks)

1. Record data from office visit if completed as standard of care
2. Record vital signs (HR/BP)
3. Record use of select medications
4. Record 12 lead ECG
5. Record Echocardiogram
6. Perform 6-minute walk test
7. Collect Rand 36-Item Health Survey (SF-36)
8. Collect Atrial Fibrillation severity Scale (AFSS)
9. Assessment of NYHA class
10. Record the data from remote arrhythmia monitoring and /or ECGs completed as a part of standard of care
11. Record the results from routine lab assessment and clinical indicated tests completed as a part of Standard of care: these may include but not limited to:
  - Blood tests, chest x-rays, pulmonary function test, Spiral CT to assess pulmonary vein stenosis (only if in the ablation arm only if clinically indicated )
12. Assessment of Adverse Events (AE) and Serious Adverse Events (SAE)
13. Record any hospitalizations including short stays and hospital admissions.

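### The protocol gives inconsistent starts for the primary endpoint window, so the two arms can be counted from different time origins

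*Combined protocol and SAP*

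**What the plan says.** The primary endpoint (Section 3.1) is a time to first event that counts only after the treatment period ends. When that period starts therefore decides which events count. The current text describes the start as follows:

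- Study Synopsis, both arms: "The treatment period will include the first 3 months post enrollment". Section 5.1 ties enrollment to consent: "Enrollment will occur when a subject signs and dates an informed consent form".
- Section 6, both arms: "The treatment period will include the first 3 months post enrollment or post procedure during which repeat ablation can be performed". No rule says which of the two dates applies.
- Section 6.1, ablation arm only: "Primary outcome data in the ablation arm will only be included in the analysis after the treatment period (three months post randomization".
- Section 6.2, drug arm: "Outcomes will be collected after the optimization of AAD". No date or time limit is attached.
- Section 3, both arms: "After the 3 month treatment period, the endpoints will be assessed for 12 months". The start of the three months is not named.
- Section 7: the Cox model is specified without a time origin.

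The last scheduled contact, in Section 6.4.2, is the "12-15 Month Post Randomization Visit (+/- 3 weeks".

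**The concern.** A time-to-event comparison between randomized arms needs one time origin, defined the same way in both. Here the only sentence that says when primary data enter the analysis covers the ablation arm alone. Section 6 permits a procedure-based start for the same period. In the drug arm, the date on which optimization ends depends on the treating physician.

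Two competent statisticians could build different primary datasets from this text. The trial is unblinded, so a choice left open until analysis could be made with outcomes in view. What is at stake is which early events count in each arm.

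**Working it through.** **The plan's own figure.** Section 7 plans 100 patients per arm for 80% power at two-sided 0.05, with event rates of 60% on drugs and 30-40% on ablation. At the 40% end, the two-proportion formula gives

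n = [1.96·√(2·0.5·0.5) + 0.842·√(0.4·0.6 + 0.6·0.4)]² / 0.20² ≈ 97 per arm,

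and 100 per arm gives 81.2% power. The sample size reproduces and is not part of the problem.

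**Step 1: the windows side by side.** Let D be the months from randomization to ablation. Treat enrollment and randomization as the same date, since the assessment schedule shows a single "Screening/ Baseline/ Randomization Visit".

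| Reading | Window opens | Window closes |
|---|---|---|
| Ablation arm, Section 6.1 | month 3 | month 15 |
| Ablation arm, post-procedure option in Section 6 | month D + 3 | month D + 15 |
| Drug arm, Section 3 or Section 6 | about month 3 | about month 15 |
| Drug arm, Section 6.2 taken literally | end of optimization, undated | not determined |

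The post-procedure option delays the ablation arm's clock. The optimization wording can delay the drug arm's clock. The two readings push in opposite directions.

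**Step 2: fit with the last visit.** Three weeks is 21/30.4 = 0.69 month, so the last visit can fall as late as month 15.69. A post-procedure window closes after that when D + 15 > 15.69, that is, when D > 0.69 month.

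**Step 3: does the anchor change the event rate?** Take the planned 40% ablation-arm rate with constant hazard: h = -ln(0.60)/12 = 0.0426 per month. Any 12-month window then gives 1 - exp(-12h) = 40%, wherever it starts. A difference appears only if the hazard is not constant.

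For illustration, *assume* that the hazard is m times higher in the first 3 months after the procedure. With the randomization anchor and D up to 3, D of those high-hazard months fall inside the window:

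rate = 1 - exp(-h·[12 + (m - 1)·D])

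| D (months) | m = 1 | m = 1.5 | m = 2 |
|---|---|---|---|
| 1 | 40.0% | 41.3% | 42.5% |
| 2 | 40.0% | 42.5% | 44.9% |
| 3 | 40.0% | 43.7% | 47.2% |

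The post-procedure anchor gives 40% throughout. If only a fraction f of the arm is ablated late, the arm-level difference is f × (rate - 40%):

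- f = 25% at D = 2: 0.6 points (m = 1.5) to 1.2 points (m = 2).
- f = 50% at D = 3: 1.9 points (m = 1.5) to 3.6 points (m = 2).

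**Step 4: an opposing effect.** Dofetilide is allowed until 2 months after ablation (Sections 5.4 and 6.1). Under the randomization anchor it can overlap the window when D + 2 > 3, that is, when D > 1. With m = 1.5 and D = 3, a patient on dofetilide has a rate of 36.0% if the drug suppresses every event during the overlap and 43.7% if it suppresses none. The direction of the net effect is therefore not fixed.

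The values of D, m, f and the degree of suppression are all assumptions. The documents give none of them.

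**The case against.** The strongest reply is that the protocol already implies the answer. Section 6.1 is explicit for the ablation arm, Section 3 describes one three-month period for both arms, and the follow-up visits are timed from randomization. Section 6 places drug titration inside the treatment period, so the optimization wording in Section 6.2 may be only a loose reference to the end of that period. Much of this stands, and it supports the randomization anchor. It does not remove the post-procedure option from Section 6, and it does not give the drug arm a stated date.

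A reader might infer several stronger points that the documents do not support:

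- **That consent and randomization dates differ enough to matter.** The single baseline and randomization visit suggests that they hardly differ.
- **That a post-procedure anchor demonstrably favours ablation.** Events in the skipped months (1 - exp(-hD), or 4.2%, 8.2% and 12.0% for D = 1, 2 and 3) look like a bias. Under constant hazard the 12-month rate is still 40%, so they do not measure one.
- **That power is seriously damaged.** Large losses appear only if an assumed delay and an assumed early hazard are applied to every ablation patient.
- **That the visit schedule permits only one anchor.** The final visit may fall as early as 12 - 0.69 = 11.3 months. A window from month 3 to month 15 is then not fully covered by that visit either.
- **That nothing limits the time to ablation.** The content under the two patient-group headings in Section 5.4 cannot be read in the available text, so no conclusion can be drawn from it in either direction.

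**Conclusion.** The point holds as a minor inconsistency between current rules. Section 6.1 conflicts with the post-procedure option in Section 6, Section 6.2 leaves the drug arm undated, and Sections 3, 3.1 and 7 do not settle the matter. Taken literally, the text allows different time origins in the two arms.

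The size and direction of any bias cannot be derived, because the ablation delay and the early hazard are not given. It is probably small. The illustrative arm-level differences run from 0.6 to 3.6 points against the planned 20, and they are zero if the hazard is constant. The conclusion that the wording conflicts depends on none of these assumptions.

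**What to change.** Fix the endpoint-counting window and leave the clinical treatment period as it is.

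1. In Sections 3, 3.1 and 7, state: *In both arms, endpoint events are counted from 3 months to 15 months after randomization, whatever the date of ablation or AAD optimization; month 3 after randomization is the time origin for the Cox model.*
2. In Section 6.2, replace the optimization wording so that outcomes run *from 3 months after randomization*.
3. In the Study Synopsis and Section 6, state that the trial (endpoint) period starts 3 months after randomization.
4. Leave unchanged the clinical period for repeat ablation and drug titration, and the per-protocol definition in Section 7.1, which depends on it. Redefining the treatment period itself would shorten the time allowed for repeat ablation in late-ablated patients and change who is in the per-protocol set.
5. Report the distribution of time from randomization to ablation, using the ablation dates already recorded on the CRF.

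The cost is wording in a few sections and one descriptive table. Treatment, visits, the intent-to-treat population and the Cox model's covariates do not change. The downside is that, in late-ablated patients, some early post-procedure events will count against ablation. The table in item 5 lets readers judge how often that could occur. The edit should be made before any outcome data are analysed.

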### 6.2 AAD Treatment

Patients randomized to AAD will receive AADs per Physician and patient preference. Initiation and ongoing clinical evaluations of drug therapy must conform to HRS/ACC/AHA/ ESC guidelines. Oral anticoagulation will follow HRS/ACC/AHA/ESC guidelines. If a patient randomized to the AAD treatment arm has an ablation during the treatment initiation period, the date of ablation will be recorded on the CRF. Outcomes will be collected after the optimization of AAD.

### 6.3 Baseline Visit

Baseline visit assessments will be completed for both arms before initiation of treatment. These include:

1. Record vital signs (HR and BP)
2. Record demographic and medical history information
3. For female subjects: Verify that the subject is post-menopausal /surgically sterile following individual site standard of care process
4. Record use of select medications
5. Record 12 lead ECG results
6. Record Echocardiogram results
7. Perform 6 minute walk test
8. Collect Rand 36-Item Health Survey (SF-36)
9. Collect Atrial Fibrillation Severity Scale (AFSS)
10. Assessment of NYHA class
11. Record the data from remote arrhythmia monitoring and /or ECGs completed as a part of standard of care
12. Record results from routine lab assessment and clinically indicated tests completed as a part of standard of care; these may include but not limited to:
  - Laboratory assessments may include CBC, PT, PTT, INR if applicable, chest x-rays, pulmonary function test, spiral CT to assess pulmonary vein stenosis (only if in the ablation arm)

CONFIDENTIAL

This document is confidential and the property of The Cleveland Clinic Foundation. No part of it may be transmitted, reproduced, published, or used by other persons without prior written authorization from the study sponsor.

V6.0\_22May2017

## 6.4 Follow Up (Month 3 through Month 15)

### 6.4.1 3-6 Months Post Randomization Visit (+/- 3 weeks)

1. Record data from office visit if completed as standard of care
2. Record vital signs (HR/BP)
3. Record use of select medications
4. Record 12 lead ECG results
5. Perform 6-minute walk test
6. Collect Rand 36-Item Health Survey (SF-36)
7. Collect Atrial Fibrillation Severity Scale (AFSS)
8. Assessment of NYHA class
9. Record the data from remote arrhythmia monitoring and /or ECGs completed as a part of standard of care
10. Record the results from routine lab assessment and clinically indicated tests completed as a part of Standard of care: these may include but not limited to:
  - Blood tests, chest x-rays, pulmonary function test, Spiral CT to assess pulmonary vein stenosis (only if in the ablation arm)
11. Assessment of Adverse Events (AE) and Serious Adverse Events (SAE)
12. Record any hospitalizations including short stays and hospital admissions.

### 6.4.2 12-15 Month Post Randomization Visit (+/- 3 weeks)

1. Record data from office visit if completed as standard of care
2. Record vital signs (HR/BP)
3. Record use of select medications
4. Record 12 lead ECG
5. Record Echocardiogram
6. Perform 6-minute walk test
7. Collect Rand 36-Item Health Survey (SF-36)
8. Collect Atrial Fibrillation severity Scale (AFSS)
9. Assessment of NYHA class
10. Record the data from remote arrhythmia monitoring and /or ECGs completed as a part of standard of care
11. Record the results from routine lab assessment and clinical indicated tests completed as a part of Standard of care: these may include but not limited to:
  - Blood tests, chest x-rays, pulmonary function test, Spiral CT to assess pulmonary vein stenosis (only if in the ablation arm only if clinically indicated )
12. Assessment of Adverse Events (AE) and Serious Adverse Events (SAE)
13. Record any hospitalizations including short stays and hospital admissions.

## 7 Statistical Analysis

A Cox proportional hazards regression model adjusting for site and randomization strata will be used to test for treatment group differences in the primary endpoint. Kaplan-Meier estimates and curves will also be created. Secondary endpoints will be analyzed using a two-sample t-test or Wilcoxon signed rank as appropriate. Depending on the distribution for the total number of hospitalizations it will be treated as a continuous variable or collapsed into categories (0-2, 3-5, 5-7, >7). The intent-to-treat population will be used for all analysis. Patients who drop-out before study completion due to cardiac causes will be considered as having an event at the time drop-out for the primary analysis. Patients who drop-out for other reasons will be treated as censored observations at the time of drop-out in the primary analysis. Analysis based on the protocol and safety populations will also be done. All statistical tests will be two-sided and an alpha of 0.05 or less will be considered statistically significant. Mean and

CONFIDENTIAL

This document is confidential and the property of The Cleveland Clinic Foundation. No part of it may be transmitted, reproduced, published, or used by other persons without prior written authorization from the study sponsor.

V6.0\_22May2017

standard deviation or frequency and percent will be used to describe demographics, medical history and other baseline variables by treatment group. T-tests or chi-square tests as appropriate will be used to compare the baseline factors by treatment group.

Sample size is based on an expected 30-40% rate of hospitalization for recurrence of AF, heart failure or DC conversion at 12 months in the ablation arm and a 60% rate at 12 months in the AAD arm. One hundred patients per treatment arm are needed to have 80% power at an alpha level of 0.05 to detect this difference. Assuming a 10% drop-out rate, a total of 220 patients will need to be enrolled. Randomization will be 1:1 based on EF stratification EF  $\leq$ 35% and >35%.

**Safety population:** All patients that received any ablation treatment **or at least 1 dose of AAD** will be included in the safety population.

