Statistical Methodology	Sample size is based on an expected 30-40% AF recurrence rate at 12 months in the ablation arm and a 60% AF recurrence rate at 12 months in the AADs. One hundred patients per treatment arm are needed to have 80% power at an alpha level of 0.05 to detect this difference. Assuming a 10% drop-out rate, a total of 220 patients will need to be enrolled. Randomization will be 1:1 based on EF stratification EF $\leq$ 35% and >35%. A Cox proportional hazards regression model adjusting for site and EF strata will be used to test for treatment group differences in the primary endpoint.

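### The primary Cox model leaves out baseline antiarrhythmic drug status; prespecifying it would cost almost nothing and could add a small amount of power

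*Combined protocol and SAP*

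**What the plan says.** Section 7 gives the primary model: "A Cox proportional hazards regression model adjusting for site and randomization strata will be used to test for treatment group differences". The Statistical Methodology row of the Study Synopsis names the stratum: "A Cox proportional hazards regression model adjusting for site and EF strata will be used to test for treatment group differences". The two agree, because EF (35% or below vs above 35%) is the only stratification factor the documents name: "Randomization will be 1:1 based on EF stratification EF".

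Section 5.4 gives separate handling around ablation for patients who enter on dofetilide or on other AADs. It also carries two headings, "Anti-Arrhythmic Drug (AAD) Naïve patients" and "Patients already on AADs". What stood under them is not in the text available here.

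The Study Assessments table has medications recorded at baseline. Section 6.3 words the item as "Record use of select medications", without listing which drugs. The plan neither considers nor rejects AAD status as a covariate.

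On size and error rate, Section 7 states "One hundred patients per treatment arm are needed to have 80% power at an alpha level of 0.05" and "All statistical tests will be two-sided and an alpha of 0.05 or less will be considered statistically significant".

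**The concern.** AAD therapy is the control treatment, so a patient already on an AAD at entry has already been exposed to it. It is plausible that such a patient has a different risk of recurrence, and in particular a different outlook on further AAD therapy, from a naive patient.

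If that is so, two things follow. First, in a Cox model, omitting a prognostic factor pulls the treatment hazard ratio toward 1 and costs some power even when the arms are balanced. Second, AAD status is not a named stratum, so nothing in the allocation holds it in balance with about 100 patients per arm.

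Section 7 plans tests of baseline factors between arms but does not say what would follow if one differed. In an unblinded trial, an adjustment for AAD status chosen after the data are seen would be open to challenge. The same adjustment prespecified would not be.

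**Working it through.** **The plan's own figure.** Inputs from Section 7: 12-month event rates of 30–40% (ablation) and 60% (AAD), 80% power, two-sided alpha 0.05. At 40% vs 60%:

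n = [1.96·√(2·0.5·0.5) + 0.8416·√(0.4·0.6 + 0.6·0.4)]² / 0.20² = (1.386 + 0.583)² / 0.04 ≈ 97 per arm.

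Power with 100 per arm is 81.2%, so the stated figure reproduces at the 40% end. At 35% the power is 94.9% and at 30% it is 99.2%. A covariate can therefore add at most about 5 points at 35% and under 1 point at 30%. The gains below apply at the 40% end.

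**Simulation set-up.** 200 patients 1:1, exponential times, 12 months of follow-up, Cox Wald test at two-sided 0.05, 3,000 trials per cell. Assumed, because the documents are silent: prevalence π of prior AAD use, and its prognostic hazard ratio h. In each arm the hazard λ solves

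(1 − π)·exp(−λ) + π·exp(−λh) = 1 − p, with p = 0.60 (AAD) or 0.40 (ablation),

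so the marginal rates stay at the plan's values. With h = 1 the treatment hazard ratio is ln(0.6)/ln(0.4) = 0.557.

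| π | h | Power without | Power with | Gain (points) | SE without | SE with |
|---|---|---|---|---|---|---|
| 30% | 1.0 | 82.7% | 82.7% | 0.0 | 0.2055 | 0.2062 |
| 30% | 1.25 | 82.9% | 83.1% | 0.2 | 0.2057 | 0.2064 |
| 30% | 1.5 | 83.1% | 84.1% | 1.0 | 0.2057 | 0.2064 |
| 30% | 2.0 | 82.8% | 84.7% | 1.9 | 0.2053 | 0.2063 |
| 30% | 3.0 | 82.7% | 89.1% | 6.4 | 0.2057 | 0.2073 |
| 50% | 1.0 | 82.8% | 82.7% | −0.1 | 0.2057 | 0.2063 |
| 50% | 1.25 | 82.6% | 82.9% | 0.3 | 0.2057 | 0.2063 |
| 50% | 1.5 | 82.8% | 83.5% | 0.7 | 0.2056 | 0.2063 |
| 50% | 2.0 | 83.2% | 86.2% | 3.0 | 0.2055 | 0.2063 |
| 50% | 3.0 | 82.7% | 89.2% | 6.5 | 0.2059 | 0.2070 |

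SE is the mean standard error of the log hazard ratio. The Monte Carlo error of each gain is 0.2 to 0.5 points.

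**Where the gain comes from.** At π = 50%, h = 2, the mean log hazard ratio moves from −0.591 to −0.616. The ratio of estimate to SE goes from 0.591/0.2055 = 2.88 to 0.616/0.2063 = 2.99. At h = 3 it goes from 0.593/0.2059 = 2.88 to 0.650/0.2070 = 3.14. The SE rises slightly in every cell, and the coefficient moves further from zero.

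**With the planned covariates in the model.** Adding an EF term and six site terms (the number of sites is assumed) gives the same picture. With a non-prognostic covariate, power is 81.7% vs 81.7% at 30% prevalence and 80.6% vs 80.5% at 50%. Gains are about 1 point at h = 1.5, 2.5–3 at h = 2 and 5–6 at h = 3.

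**Chance imbalance.** The SD of the between-arm difference in prevalence is √(2π(1 − π)/100).

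- At 50% prevalence this is 0.0707. A difference of 10 points or more in either direction has z = 0.10/0.0707 = 1.41, probability about 16%.
- At 30% it is 0.0648, z = 1.54, probability about 12%.

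About half of these would go against ablation and half would flatter it. If prior AAD use is 55% in the ablation arm and 45% in the AAD arm (2,000 trials per cell):

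| h | Power unadjusted | Power adjusted | Unadjusted HR | True conditional HR |
|---|---|---|---|---|
| 1.5 | 78% | 84% | – | – |
| 2 | 74% | 86% | 0.59 | 0.54 |
| 3 | 68% | 90% | 0.62 | 0.52 |

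These figures are conditional on that imbalance. The first table drew AAD status at random in each trial, so it already averages over imbalances, and the two sets of gains must not be added.

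**The case against.** The strongest reply is that nothing here is wrong with the plan. The test is valid without the covariate, the sample size does not depend on it, and power at 100 per arm already exceeds 80%. The size of any benefit rests on a prevalence and a prognostic strength that no section supplies, and at a hazard ratio of 1.5 or below the gain is negligible. The factors that Section 1.1 itself links to outcome are paroxysmal vs persistent AF, length of AF history and episode duration. An AAD at entry need not mean that the drug failed: the inclusion criteria ask for symptomatic AF documented within 12 months, and the drug may have been started afterwards. All of this stands. It limits the point to an optional improvement.

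Three stronger readings are tempting and are not supported.

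- A reader might infer from the two headings in Section 5.4 that randomization is split by AAD status. Every statement of the allocation names EF alone, and the content under the headings is missing here. If AAD status were a stratum, Section 7's adjustment for randomization strata would already cover it.
- A reader might expect a gain in precision. The standard error rises slightly; what can improve is power.
- A reader might call the change free. It adds a parameter to a model that already carries site terms, and it changes the target to a hazard ratio conditional on AAD status (0.544 rather than about 0.557 at a prognostic hazard ratio of 2). The planned model is already conditional on site and EF, so this is a small step.

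What the reply does not remove is that the covariate costs essentially no power when it is useless, and helps when it is not.

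**Conclusion.** The point holds as a minor improvement. The primary model omits a plausible prognostic factor that bears directly on the comparator and is probably already recorded. At 40% vs 60%, 100 per arm and an assumed 30–50% prevalence, including it is worth about 0–1 point of power at a prognostic hazard ratio of 1.5 or less, 2–3 points at 2 and 5–7 points at 3. The gain is smaller still if the ablation rate is nearer 30%. Prespecification also settles in advance how a chance imbalance in AAD status is handled, whichever arm it favours.

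The omission does not bias the planned test or undermine the sample size. Nor does the argument extend to the secondary endpoints: Section 7 assigns them a t-test or Wilcoxon test, so there is no regression model for AF recurrence to which the term could be added. Nothing here makes a case for displaying results by AAD group.

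**What to change.** In Section 7, and in the matching line of the synopsis, add baseline AAD status (naive vs already on an AAD, determined before assigned treatment starts) as a prespecified covariate in the primary Cox model beside site and EF stratum. Confirm in Section 6.3 that AADs are among the medications recorded at baseline, since the wording there does not list them.

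The cost is one line of text and one model parameter, with a standard error larger by roughly 0.001 and a hazard ratio that is also conditional on AAD status. Randomization and sample size do not change. If AADs prove not to be among the recorded items, one baseline item must be added to the case report form.
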